5.1.1 Risks Associated with Faricimab

The anticipated safety risks for faricimab are outlined below; these risks are either from the drug itself or the injection procedure.

Anticipated risks of faricimab include intraocular inflammation, the IVT injection-related risks of infectious endophthalmitis, retinal detachment/tear, and *transient* increased IOP. Potential risks *associated with faricimab include* iatrogenic traumatic cataract, *immunogenicity*, as well as the non-ocular risk of arterial thromboembolic events.

Please see the RO6867461 (faricimab) Investigator's Brochure for more details on the *safety information for* faricimab.

5.1.2 Management of Patients Who Experience Adverse Events

5.1.2.1 Dose Modifications

Dose modifications will not be performed in this study.

5.1.2.2 Treatment Interruption

If any of the dose interruption and treatment discontinuation criteria specified in Table 3 are met, treatment will be interrupted (or discontinued, if applicable) and will not be resumed earlier than the next scheduled study visit. The reason for study treatment interruption/discontinuation should be recorded on the appropriate eCRF and, if applicable, on the adverse event eCRF.

5.1.2.3 Management Guidelines

Study treatment interruption and/or patient discontinuation from the study treatment for adverse events will be determined using the criteria listed in Table 3.

Table 3 Dose Interruption and Treatment Discontinuation Criteria

Event	Criteria
Intraocular inflammation	 Interrupt study treatment if intraocular inflammation (iritis, iridocyclitis, or vitritis) is ≥ 2+ in the study eye. Study treatment may be resumed subsequently as determined by the investigator.
Cataract surgery in the study eye	 Interrupt study treatment after cataract surgery in study eye. Study treatment may be resumed no earlier than 28 days after an uncomplicated cataract surgery and no evidence of post-operational inflammation at that time. For cataract surgery with complications, study treatment may be permitted by the investigator following consultation with the Medical Monitor.
BCVA decrease	 Interrupt study treatment if there is a study treatment–related decrease in BCVA of ≥ 30 letters in the study eye compared with the last assessment of BCVA prior to the most recent treatment. Study treatment may be permitted subsequently, as determined by the investigator.
Elevated IOP	 Interrupt study treatment if pretreatment IOP in the study eye is ≥ 30 mmHg. Treatment may be permitted when IOP has been lowered to < 30 mmHg, either spontaneously or by treatment, as determined by the investigator.
Rhegmatogenous retinal break	 Interrupt study treatment if a retinal break is present in the study eye. Study treatment may be resumed no earlier than 28 days after successful laser retinopexy, as determined by the investigator.
Rhegmatogenous retinal detachment or macular hole	 Interrupt study treatment if rhegmatogenous retinal detachment or Stage 3 or 4 macular hole occurs in the study eye. Study treatment may be subsequently permitted by the investigator following consultation with the Medical Monitor.
Active or suspected infection	Interrupt study treatment if active or suspected ocular or periocular infections are present (e.g., infectious conjunctivitis, infectious keratitis, infectious scleritis, or endophthalmitis) in either eye or if the patient requires treatment for an active systemic infection. Study treatment may be interrupted for other medically significant systemic infection in consultation with Medical Monitor.
On-study prohibited medications	 Refer to Section 4.4.2 for additional reasons for potential study treatment discontinuation.

BCVA=best-corrected visual acuity; IOP=intraocular pressure.

5.2 SAFETY PARAMETERS AND DEFINITIONS

Safety assessments will consist of monitoring and recording adverse events, including serious adverse events and adverse events of special interest, performing protocol-specified safety laboratory assessments, measuring protocol-specified vital

signs, and conducting other protocol-specified tests that are deemed critical to the safety evaluation of the study.

Certain types of events require immediate reporting to the Sponsor, as outlined in Section 5.4.

5.2.1 Adverse Events

According to the ICH guideline for Good Clinical Practice, an adverse event is any untoward medical occurrence in a clinical investigation subject administered a pharmaceutical product, regardless of causal attribution. An adverse event can therefore be any of the following:

- Any unfavorable and unintended sign (including an abnormal laboratory finding), symptom, or disease temporally associated with the use of a medicinal product, whether or not considered related to the medicinal product
- Any new disease or exacerbation of an existing disease (a worsening in the character, frequency, or severity of a known condition) (see Sections 5.3.5.8 and 5.3.5.9 for more information)
- Recurrence of an intermittent medical condition (e.g., headache) not present at baseline
- Any deterioration in a laboratory value or other clinical test (e.g., ECG, X-ray) that is associated with symptoms or leads to a change in study treatment or concomitant treatment or discontinuation from study drug
- Adverse events that are related to a protocol-mandated intervention, including those that occur prior to assignment of study treatment (e.g., screening invasive procedures such as biopsies)

5.2.2 Serious Adverse Events (Immediately Reportable to the Sponsor)

A serious adverse event is any adverse event that meets any of the following criteria:

- Is fatal (i.e., the adverse event actually causes or leads to death)
- Is life threatening (i.e., the adverse event, in the view of the investigator, places the patient at immediate risk of death)

This does not include any adverse event that, had it occurred in a more severe form or was allowed to continue, might have caused death.

- Requires or prolongs inpatient hospitalization (see Section 5.3.5.10)
- Results in persistent or significant disability/incapacity (i.e., the adverse event results in substantial disruption of the patient's ability to conduct normal life functions)
- Is a congenital anomaly/birth defect in a neonate/infant born to a mother exposed to study drug

Is a significant medical event in the Investigator's judgment (e.g., may jeopardize
the patient or may require medical/surgical intervention to prevent one of the
outcomes listed above)

The terms "severe" and "serious" are not synonymous. Severity refers to the intensity of an adverse event (e.g., rated as mild, moderate, or severe, or according to National Cancer Institute Common Terminology Criteria for Adverse Events [NCI CTCAE]; see Section 5.3.3); the event itself may be of relatively minor medical significance (such as severe headache without any further findings).

Severity and seriousness need to be independently assessed for each adverse event recorded on the eCRF.

Serious adverse events are required to be reported by the Investigator to the Sponsor immediately (i.e., within \leq 24 hours after learning of the event; see Section 5.4.2 for reporting instructions).

5.2.3 Adverse Events of Special Interest (Immediately Reportable to the Sponsor)

Adverse events of special interest are required to be reported by the Investigator to the Sponsor immediately (i.e., within \le 24 hours after learning of the event; see Section 5.4.2 for reporting instructions). Adverse events of special interest for this study are as follows:

- Cases of potential drug-induced liver injury that include an elevated ALT or AST in combination with either an elevated bilirubin or clinical jaundice, as defined by Hy's Law (see Section 5.3.5.6)
- Suspected transmission of an infectious agent by the study drug, as defined below
 Any organism, virus, or infectious particle (e.g., prion protein transmitting
 transmissible spongiform encephalopathy), pathogenic or non-pathogenic, is
 considered an infectious agent. A transmission of an infectious agent may be
 suspected from clinical symptoms or laboratory findings that indicate an
 infection in a patient exposed to a medicinal product. This term applies only
 when a contamination of the study drug is suspected.
- Sight-threatening adverse events: an adverse event is considered to be sight-threatening and should be reported expeditiously if it meets one or more of the following criteria:

It causes a decrease of ≥ 30 letters in VA score (compared with the last assessment of VA prior to the most recent assessment) lasting more than 1 hour.

It requires surgical or medical intervention (i.e., conventional surgery, vitrectomy, vitreous tap, or biopsy with IVT injection of anti-infective treatments, or laser or retinal cryopexy with gas, or a medication) to prevent permanent loss of sight.

It is associated with severe intraocular inflammation (i.e., endophthalmitis, 4 +AC cell/flare, or 4 +vitritis; see Section 5.3.5 and Appendix 3 for intraocular inflammation grading scales).

All of the above listed sight-threatening adverse events should be reported as serious adverse events, listing the underlying cause (if known) of the event as the primary event term.

5.3 METHODS AND TIMING FOR CAPTURING AND ASSESSING SAFETY PARAMETERS

The Investigator is responsible for ensuring that all adverse events (see Section 5.2.1 for definition) are recorded on the Adverse Event eCRF and reported to the Sponsor in accordance with instructions provided in this section and in Sections 5.4 through 5.6.

For each adverse event recorded on the Adverse Event eCRF, the Investigator will make an assessment of seriousness (see Section 5.2.2 for seriousness criteria), severity (see Section 5.3.3), and causality (see Section 5.3.4).

Please note, throughout the entire study period, the retinal physician is expected to assess adverse events, which includes assigning causality and severity of the event.

5.3.1 Adverse Event Reporting Period

Investigators will seek information on adverse events at each patient contact. All adverse events, whether reported by the patient or noted by study personnel, will be recorded in the patient's medical record and on the Adverse Event eCRF.

After informed consent has been obtained but prior to initiation of study drug, only serious adverse events caused by a protocol-mandated intervention (e.g., invasive procedures such as biopsies, discontinuation of medications) should be reported (see Section 5.4.2 for instructions for reporting serious adverse events).

After initiation of study drug, all adverse events will be reported until the SFV (≥28 to <35 days from last study treatment). For patients who terminate study treatment and from the study early, all adverse events will be reported up to the ETV. For patients who discontinue study treatment early but continue to participate in the study, adverse events will be reported until their last or final study visit.

Instructions for reporting adverse events that occur after the adverse event reporting period are provided in Section 5.6.

5.3.2 Eliciting Adverse Event Information

A consistent methodology of non-directive questioning should be adopted for eliciting adverse event information at all patient evaluation timepoints. Examples of non-directive questions include the following:

- "How have you felt since your last clinic visit?"
- "Have you had any new or changed health problems since you were last here?"

5.3.3 Assessment of Severity of Adverse Events

Table 4 provides guidance for assessing adverse event severity.

Table 4 Adverse Event Severity Grading Scale

Severity	Description
Mild	Discomfort noticed, but no disruption of normal daily activity
Moderate	Discomfort sufficient to reduce or affect normal daily activity
Severe	Incapacitating with inability to work or to perform normal daily activity

Note: Regardless of severity, some events may also meet seriousness criteria. Refer to definition of a serious adverse event (see Section 5.2.2).

5.3.4 Assessment of Causality of Adverse Events

Investigators should use their knowledge of the patient, the circumstances surrounding the event, and an evaluation of any potential alternative causes to determine whether an adverse event is considered to be related to the study drug, indicating "yes" or "no" accordingly. The following guidance should be taken into consideration (see Table 5):

- Temporal relationship of event onset to the initiation of study drug
- Course of the event, with special consideration of the effects of dose reduction, discontinuation of study drug, or reintroduction of study drug (as applicable)
- Known association of the event with the study drug or with similar treatments
- Known association of the event with the disease under study
- Presence of risk factors in the patient or use of concomitant medications known to increase the occurrence of the event
- Presence of non-treatment-related factors that are known to be associated with the occurrence of the event

Table 5 Causal Attribution Guidance

Is the adverse event suspected to be caused by the study drug on the basis of facts, evidence, science-based rationales, and clinical judgment?

- YES There is a plausible temporal relationship between the onset of the adverse event and administration of the study drug, and the adverse event cannot be readily explained by the patient's clinical state, intercurrent illness, or concomitant therapies; and/or the adverse event follows a known pattern of response to the study drug; and/or the adverse event abates or resolves upon discontinuation of the study drug or dose reduction and, if applicable, reappears upon re-challenge.
- An adverse event will be considered related, unless it fulfills the criteria specified below. Evidence exists that the adverse event has an etiology other than the study drug (e.g., preexisting medical condition, underlying disease, intercurrent illness, or concomitant medication); and/or the adverse event has no plausible temporal relationship to administration of the study drug (e.g., cancer diagnosed 2 days after the first dose of study drug).

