Complications for AH sampling reported in the literature are traumatic injuries of the iris, hyphema, inflammation, infection, and hypotension. The reported complication rates are between 0.01% and 0.7% with no long-term sequelae and no effect on VA (Saxena et al. 2019; Trivedi et al. 2011). There is also a small risk of induction of traumatic cataract associated with AC paracentesis (Pleyer and Garweg 2008).

The planned multimodal imaging assessments are considered as part of the current SOC. They are routinely used in the clinic for diagnosis, assessment of the disease course, response to treatment, and for research purposes to better understand the underlying disease pathology. All instruments used will be American National Standards Institute compliant.

Based on the results of the Phase II study (BP30099 [BOULEVARD]), the 6-mg dose of faricimab has the potential for superior efficacy outcomes in DME and the potential for prolonged treatment duration while achieving and maintaining comparable efficacy when compared to SOC IVT. Besides close monitoring and treatment with faricimab, no other direct benefits are foreseen for the patients. However, patients in this study will provide AH biomarker samples and associated data to generate algorithms that could potentially lead to a more personalized treatment option for future patients.

In the setting of the coronavirus 2019 (COVID-19) pandemic, patients with comorbidities including those patients with diabetes are a more vulnerable population. Infection with severe acute respiratory syndrome coronavirus 2 (SARS-CoV-2) has been associated with higher morbidity and mortality in patients with diabetes in some retrospective analysis. Susceptibility to infection with diabetes may be argued, but infection once acquired is likely to be more severe and prolonged, determined by a number of factors, including duration of diabetes, the presence of diabetes-related complications, and the level of glycemic control. It is not anticipated that faricimab will increase the risk of infection with SARS-CoV-2. Four Phase 3 clinical trials (2 in DME and 2 in nAMD) with faricimab are ongoing during this pandemic, and to date these studies have not shown any increased risk of developing COVID-19 or of having a worse outcome in patients on faricimab, however this will continue to be monitored.

2. OBJECTIVES AND ENDPOINTS

The exploratory objective and the endpoints are provided in Table 1.

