5.5 FOLLOW-UP OF PATIENTS AFTER ADVERSE EVENTS

5.5.1 Investigator Follow-Up

The Investigator should follow each adverse event until the event has resolved to baseline grade or better, the event is assessed as stable by the Investigator, the patient is lost to

follow-up, or the patient withdraws consent. Every effort should be made to follow all serious adverse events considered to be related to study drug or trial-related procedures until a final outcome can be reported.

During the study period, resolution of adverse events (with dates) should be documented on the Adverse Event eCRF and in the patient's medical record to facilitate source data verification.

All pregnancies reported during the study should be followed until pregnancy outcome.

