- 4. If the start date is completely missing, but the AE is either ongoing or the end date is after the first dose date then impute the start date as the first dose date.
- 5. For any cases involving the rules above, if the AE end date is before the AE start date, then leave the AE start date missing and assume that AE is treatment emergent for the purpose of the analysis. Further, if the AE end date is complete and occurs prior to first dose date, leave the AE start date missing and assume that AE is not treatment emergent.

Output Conventions

All analyses of AE data will be performed using the PTs unless otherwise specified.

For all summary tables, the AEs will be sorted by SOC (in decreasing order of overall incidence) and then by PT (in decreasing order of overall incidence). All summaries and listings of AEs will be based on the Safety-evaluable population. Summaries of AEs will be generated to summarize the incidence of treatment emergent AEs only (TEAE and AE are used exchangeable).

Frequency tables, including patient incidence rates will be provided for the events listed below. For ocular AEs, events in the study eye and fellow eye will be summarized separately:

Overview of AE, including

- Ocular AEs and Serious ocular AEs (SAEs)
- Non-Ocular AEs and Serious non-ocular AEs (SAEs)
- Ocular AEs and SAEs leading to study drug discontinuation
- Non-Ocular AEs and SAEs leading to study drug discontinuation
- Adverse events of special interest defined as follows:
 - Case of an elevated ALT or AST in combination with either an elevated bilirubin or clinical jaundice, as defined in protocol
 - Suspected transmission of an infectious agent by the study drug
 - Causes a decrease of >= 30 letters in VA Score lasting more than 1 hour
 - Requires surgical or medical intervention to prevent permanent loss of sight
 - Associated with severe intraocular inflammation
- Ocular AEs and Serious AEs (SAEs) related to the study treatment (only for study eye)
- Ocular AEs and Serious AEs (SAEs) related to the Anti-VEGF therapy (only for fellow eye)
- Non-Ocular ATE (Arterial Thromboembolic Events) and Cerebrovascular

Hemorrhagic

- AEs of Intraocular Inflammation
- AEs of retinal vascular occlusive disease
- Deaths
- AE of Infectious endophthalmitis
- AE of Rhegmatogeneous retinal detachment
- AE of Retinal tear
- AE leading to study discontinuation

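### Causality is defined only against faricimab, so complications of the mandatory aqueous humor tap may be counted as drug-related and are not reported in their own right

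*Protocol*

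**What the plan says.** Protocol 5.3.4 tells the investigator to "determine whether an adverse event is considered to be related to the study drug", answering yes or no. Table 5 starts from yes: "An adverse event will be considered related, unless it fulfills the criteria specified below". The answer becomes no where "Evidence exists that the adverse event has an etiology other than the study drug (e.g., preexisting medical condition, underlying disease, intercurrent illness, or concomitant medication" applies, or where the timing is implausible. The investigator must also make "an evaluation of any potential alternative causes" and consider the "Presence of non-treatment-related factors that are known to be associated with the occurrence of the event". No study procedure is named among the alternatives.

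Elsewhere the protocol treats relation to a procedure as a separate idea. Section 5.2.1 counts events caused by a protocol-mandated intervention as adverse events. Section 5.3.1 uses the same idea for serious events before the first dose. Section 5.5.1 asks for follow-up of "all serious adverse events considered to be related to study drug or trial-related procedures until a final outcome can be reported".

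SAP 4.6.2 plans a table of "Ocular AEs and Serious AEs (SAEs) related to the study treatment (only for study eye") and a fellow-eye table of events related to anti-VEGF therapy. It plans none for the tap.

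On the tap itself, Protocol 1.3.2 states: "Complications for AH sampling reported in the literature are traumatic injuries of the iris, hyphema, inflammation, infection, and hypotension". It gives complication rates of 0.01% to 0.7% and adds a small risk of traumatic cataract. Protocol 4.5.7.1 makes the tap mandatory, in the study eye, immediately before the injection and by the same operator. It is done on Day 1 and Day 112, before injections 1 and 5.

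**The concern.** The tap and the injection share an eye, an operator and nearly a time point, and some of their harms have the same name. Protocol 5.1.1 lists intraocular inflammation, infectious endophthalmitis and iatrogenic traumatic cataract as anticipated or potential risks of faricimab or its injection. Protocol 1.3.2 lists inflammation, infection and traumatic cataract for the tap. For such an event after Day 1 or Day 112, the only recorded judgement defined in 5.3.4 is about the drug, and doubt resolves to yes.

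Two things are at stake. First, the study-eye table of treatment-related events may contain tap complications. The investigator's causality call also feeds the Sponsor's reporting decisions under Protocol 5.7, where expectedness is judged against the faricimab Investigator's Brochure. Second, the tap is a research procedure, and beyond monitoring and faricimab treatment Protocol 1.3.2 foresees no other direct benefit to the patient. The study should be able to state that procedure's harms, and the plan has no output that does so.

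The point concerns how recorded events are attributed, not which events are recorded.

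**Working it through.** The plan gives no figure to reproduce here. The check has two parts.

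**The text**

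- Object of the causality question (Protocol 5.3.4): study drug only.
- Default (Table 5): related, unless there is evidence of another etiology or no plausible timing. The list of other etiologies is open, so the tap is allowed as a reason for no but is not named.
- Meaning of no: not the drug. It does not identify the tap, because underlying disease or a concomitant medication gives the same answer.
- Use of procedure-relatedness (Protocol 5.2.1, 5.3.1, 5.5.1): assumed to be known, but 5.3.4 gives no guidance on recording it.
- Output (SAP 4.6.2): one study-eye attribution, to study treatment. A tap complication starting on Day 1 is treatment-emergent by date, so it enters these tables.

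The gap is therefore internal to the documents: the protocol relies on a judgement that its causality section does not define and its SAP does not tabulate.

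**The size**

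Inputs: 99 patients (SAP 2.3), 2 taps each (Protocol 3.1.1), complication rate p from 0.0001 to 0.007 (Protocol 1.3.2). Assumptions: the rate is per tap, taps are independent, and every patient has both taps.

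- Taps: 99 × 2 = 198.
- Expected complications, 198 × p: 198 × 0.0001 = 0.02; 198 × 0.007 = 1.39.
- Chance of at least one, 1 − (1 − p)^198: 1 − 0.9999^198 = 0.020; 1 − 0.993^198 = 0.751.
- With 60 patients (120 taps): 0.012 to 0.84 expected; chance of at least one 1.2% to 57.0%.
- Largest shift in the per-patient related-event rate, if every complication fell in a different patient and was marked drug-related: 1.39 / 99 = 1.4 percentage points.

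For a rare event type, one misattribution turns 0/99 into 1/99 (1.0%). The exact two-sided 95% upper limit for 0/99 is 1 − 0.025^(1/99) = 3.7%. For 1/99 it is the p that solves (1 − p)^99 + 99p(1 − p)^98 = 0.025, which is 5.5%.

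These counts cover complications of any type in the quoted range, including iris injury, hyphema and hypotension, which hardly overlap with the listed faricimab risks. The overlapping share is not given, and an event must also be answered yes to be misattributed. The figures are thus an upper bound on misattributed events within that range. The protocol gives no rate for traumatic cataract, which it mentions separately.

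**The case against.** A reader might infer that tap complications are counted as faricimab-related as a rule and can never be separated. The documents do not support that. Table 5 allows no on evidence of another cause, its examples are illustrative, alternative causes must be weighed, and Protocol 5.3 expects a retinal physician to judge. A recognised tap complication can be marked unrelated to faricimab. Partial separation is also possible: the date and time of each tap are recorded, four of the six injection visits have no tap, and hyphema and iris injury are recognisable by their terms.

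Nor can one infer that no data field exists. The Adverse Event eCRF is not among the documents, and the planned fellow-eye anti-VEGF table shows that attribution beyond 5.3.4 is foreseen.

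It is also fair to say that the effect is small, that safety is descriptive with no hypothesis attached, and that the SAP tables of intraocular inflammation and infectious endophthalmitis do not depend on relatedness. A second item will sometimes return both.

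All of this limits the point without removing it. A no never says that the tap was the cause. Comparing tap with non-tap visits is confounded, because the Day 1 tap always coincides with the first injection, and the SAP plans no such comparison. An answer of both is still more informative than an unqualified yes.

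**Conclusion.** The concern holds in a limited form. Protocol 5.3.4 and SAP 4.6.2 give no causality category and no summary for the AH tap, although the protocol uses procedure-relatedness elsewhere. Overlapping study-eye events after Day 1 or Day 112 may be attributed to faricimab, and the tap's own harms are not reported.

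The size is modest: 0.02 to 1.4 expected complications of any type, and a 2% to 75% chance of at least one. The width comes from the protocol's 70-fold range of rates (0.7% / 0.01%), and the top figure should not be read as the likely one. The result rests on a per-tap rate, independence and two taps in all 99 patients. No conclusion of the trial turns on it. It is a cheap improvement in what the study can say about its research procedure.

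**What to change.** - **Protocol 5.3.4 and the Adverse Event eCRF:** for study-eye ocular events, add an item on relation to AH paracentesis (yes/no), answered independently of the drug item. If the eCRF already holds such a field, only the guidance needs to change. Name the tap among the alternative etiologies in Table 5.
- **SAP 4.6.2:** tabulate study-eye ocular adverse events as drug-related only, tap-related only and both. Show onset after tap visits against onset after non-tap visits, noting that the Day 1 tap coincides with the first injection.
- **Events already entered:** query study-eye ocular events with onset from a tap visit up to the next scheduled visit (Day 1 to the Day 28 visit, Day 112 to the Day 140 visit). A query limited to the tap days would miss inflammation or infection that appears later.

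The cost is one field, a short change to the guidance, one table and a few queries. Re-assessment of events already entered will be late and so weaker evidence, some events will be classed as both, and a slowly developing cataract could fall outside the query window.
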